## 2.4 Endpoints

- **2.4.1 Response:** Treatment response will be measured using the immune related RECIST criteria (iRECIST) which are a minor modification of RECIST 1.1 for immunotherapy [91].
- **2.4.2 Death:** Death due to any cause, although in mRCC patient population, the overwhelming majority is expected to be secondary to disease progression.
- **2.4.3 Progression:** Progression will be defined according to the iRECIST criteria and verified by a second set of imaging at least 6 weeks apart.
- **2.4.4 Immune Response:** Immune response will be measured using ELISpot assay, T-cell proliferation assay and ELISA.
- 2.4.5 Toxicity: Toxicity will be measured using CTAE v4.0
- **2.4.6 HRQoL**: HRQoL will be measured using FACT-G, EQ-5D and FKSI questionnaire at baseline, after HD IL-2, and at four-month intervals after treatment.
- 2.4.7 **Cost-effectiveness analysis**: Health care utilization data needed to assess costs will be obtained from treatment records to include costs of hospitalization, treatment, ER visits, physician and clinic visits and medications. Markov modeling with probabilistic sensitivity analysis will be used to correlate quality-adjusted survival and cost.

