## 3.1 Inclusion Criteria

- 3.1.1 Pathologic evidence of clear cell RCC
- 3.1.2 Radiographic evidence of metastatic disease. CT and Bone Scan must be performed with 21 days (+ 7 days) of registration. MRI of brain can be performed within 6 months prior to registration.

3.1.2.1 Patients with any number of metastatic site are allowed to enroll. However, only up to six sites will be selected for SBRT treatment, at the discretion of the treating radiation oncologist.

- 3.1.3 Patient must have >1 lesion. Combined diameter of the lesions must be of size >1.5cm.
- 3.1.4 Previous treatment with surgery, radiation, chemotherapy, immunotherapy or any targeted agents are allowed provided that:

3.1.4.1 Chemotherapy was administered > 28 days before the start of HD IL-2 3.1.4.2 Surgery, radiation, immunotherapy or any targeted agents was administered > 14 days before the start of HD IL-2

- 3.1.5 Age  $\geq$  18 years.
- 3.1.6 Performance status ECOG 0, 1.
- 3.1.7 Patient must be eligible for HD IL-2 treatment
- 3.1.8 Patient must be eligible for SABR to one or more extra cranial sites.
- 3.1.9 Adequate organ and marrow function as defined below:
  - leukocytes ≥ 3,000/mcL
  - absolute neutrophil count ≥ 1,500/mcL
  - platelets ≥ 50,000/mcl
  - total bilirubin
- ≤ 2mg/dL
- AST(SGOT)/ALT(SPGT) ≤ 2.5 X institutional upper limit of normal
- 3.1.10 Women of child-bearing potential and men must agree to use adequate contraception (hormonal or barrier method of birth control; abstinence) prior to study entry, for the duration of study participation. Should a woman become pregnant or suspect she is pregnant while participating in this study, she should inform her treating physician immediately.
  - 3.1.10.1 A female of child-bearing potential is any woman (regardless of sexual orientation, having undergone a tubal ligation, or remaining celibate by choice) who meets the following criteria:
    - Has not undergone a hysterectomy or bilateral oophorectomy; or
    - Has not been naturally postmenopausal for at least 12 consecutive months (i.e., has had menses at any time in the preceding 12 consecutive months).
- 3.1.11 Ability to understand and the willingness to sign a written informed consent
- 3.1.12 Adequate Renal function with  $Cr \le 1.6 \text{ mg/dL}$ .
- 3.1.13 Adequate cardiac function (adequate perfusion; no ischemia) on thallium (or Tc) stress test
- 3.1.14 Adequate pulmonary function on PFT (FEV1 >65%; DLCO>60%).

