The SABR prescription dose will be delivered to the periphery of the planning target volume (PTV, see below for definitions). Investigators will have discretion in choosing from either of the biologically equivalent dose levels using one or three fractions, although a single fraction is preferred over three fraction treatments. Treating physician will have further discretion in selecting the number and location of sites to treat if >6 sites of disease are present. Maximum number of lesions treated is deemed as feasible per the treating radiation oncologist. Physician's will be **REQUIRED** to leave at least one site of disease for the purpose of measuring a radiographic response (see section 6.1) at a non-treated site, as this is part of the primary endpoint. If left untreated, this site can be treated once patient meets the definition of progressive disease (PD) (see section 6). To clarify the definition of "site", each site is an area or organ with active extracranial disease (</=3 in the liver = one site and </=3 in the lung= one site) identified by CT scan, or PET/CT, within 4 weeks prior to initiation of SBRT (up to 2 contiguous vertebral metastasis will be considered a single site of disease). For example: a patient with 4 right axillary lymph nodes, L1-L2 bone metastasis, 3 right lung lesions, 1 left lung lesion, 2 liver lesions, and T2-T3 bone metastasis would be defined as having 6 sites of disease. Preference should be given to the largest feasible disease site, symptomatic sites and sites where palliative and preventative (i.e. to prevent a pathologic fracture in weight bearing bone, impending cord compression, impending SVC compression etc.) indications are applicable. The gross target/tumor volume (GTV) should be at least 2cm^3 in size, corresponding to roughly a 1.5 cm diameter tumor. This is to ensure that adequate tumor volume and therefore adequate tumor cells (roughly 10^8 -10^9 cells/cm^3 [96]) are killed for antigen presentation. Treating physicians should choose their dose based on established planning guidelines at their center including their ability to respect normal tissue tolerance listed below. It is not required that all targets be treated with the same dose fractionation. A dose from the following table should be used:

	Total Cumulative Dose Encompassing 95% of Planning					
	Target Volume (Gy)					
Number of	Protocol Compliant Minor Deviation * MinorDeviation					
Fractions						

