## 6.0 Measurement of Effect

## 6.1 Antitumor Effect

For the primary endpoint, response and progression will be evaluated in this study using the new international criteria proposed by the Response Evaluation Criteria in Solid Tumors (RECIST) Committee [JNCI 92(3):205-216, 2000], which was also used by the two randomized trials of HD IL-2 being used as historic controls for this trial [35, 36]. The only change from RECIST v.1.1 being implemented in this study is a confirmation of new lesions or progressive disease (PD) by a second scan >6wks apart, based on the immune RECIST (irRC) criteria proposed by Wolchok. et. al that is appropriate for immune-related treatment response [91]. This is primarily because immune response often can take longer time as compared to chemotherapy before producing a radiographic response and during this time new lesions may arise which will eventually regress and if it were not for a second confirmation, these patients would be labeled to have failed therapy. In addition, the majority of mRCC responders to HD IL-2 usually produce a durable response (median response duration of 24 months), therefore, this change will not affect the outcome [35]. Additional criteria for bone lesions and clinical endpoints of pathologic fracture and cord compression are added to this study (see Section 6.1.4).

Changes in only the largest diameter (unidimensional measurement) of the tumor lesions are used in the RECIST v1.1 criteria outlined in http://www.recist.com/.

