#### 6.1.2 Disease Parameters

Measurable disease. Measurable lesions are defined as those that can be accurately measured in at least one dimension (longest diameter to be recorded) as  $\geq$ 10 mm with spiral (Helical) CT scan. All tumor measurements must be recorded in millimeters (or decimal fractions of centimeters).

Non-measurable disease. All other lesions (or sites of disease), including small lesions (longest diameter <20 mm with conventional techniques or <10 mm using spiral CT scan), are considered non-measurable disease. Bone lesions, leptomeningeal disease (patients excluded), ascites, pleural/pericardial effusions, lymphangitis cutis/pulmonis, inflammatory breast disease, abdominal masses (not followed by CT or MRI), and cystic lesions are all non-measurable.

Target lesions. All measurable lesions up to a maximum of 3 lesions per organ and 6 lesions in total, representative of all involved organs, should be identified as **target lesions** and recorded and measured at baseline. Target lesions should be selected on the basis of their size (lesions with the longest diameter) and their suitability for accurate repeated measurements (either by imaging techniques or clinically). A sum of the longest diameter (LD) for all target lesions will be calculated and reported as the baseline sum LD. The baseline sum LD will be used as reference by which to characterize the objective tumor response.

Note: Lesions receiving SABR will be called "treated lesion" which should not be confused with "target lesions" defined here for the for the purpose of radiographic measurement. Treated lesions and target lesions are mutually exclusive lesions. Therefore, treated lesions will not be used as target lesions for evaluating response. Since patients with ANY number of metastasis is eligible for this study, in the instance where patient has only one or few site of disease and all of them are treated, appearance of new lesions (either measurable or non-measureable) will constitute PD.

Non-target lesions. All other lesions (or sites of disease) including any measurable lesions over and above the 6 target lesions should be identified as **non-target lesions** and should also be recorded at baseline. Measurements of these lesions are not required, but the presence or absence of each should be noted throughout follow-up.

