## 6.1.3 Methods for Evaluation of Measurable Disease

All measurements will be done digitally on the PACs system. All baseline evaluations should be performed as closely as possible to the beginning of treatment and never more than 14 days before the beginning of the treatment.
The same method of assessment and the same technique should be used to characterize each identified and reported lesion at baseline and during follow-up using appropriate radiologic imaging.

Bone scans and CT scan of Chest, abdomen and pelvis with IV contrast will be performed at baseline. Since bone scan is not reliable for RCC, it will only be used to evaluate overall response when positive in baseline scan, and any new lesions found on bone scan must be verified with a CT.

Spiral CT and MRI. All CT scans will be Spiral CT and should be performed using a 5 mm contiguous reconstruction algorithm.

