#### 6.1.4 Response Criteria

#### 6.1.4.1 Evaluation of Target Lesions

Complete Response (CR): Disappearance of all target lesions, determined by two separate observations conducted not less than 4 weeks apart. There can be no appearance of new lesions.

Partial Response (PR): At least a 30% decrease in the sum of the longest diameter (LD) of target lesions, taking as reference the baseline sum LD. There can be no appearance of new lesions.

Progressive Disease (PD): At least a 20% increase in the sum of the LD of target lesions, taking as reference the smallest sum LD recorded since the treatment started, or the appearance of one or more new lesions verified by a second scan > 6 weeks apart.

Stable Disease (SD): Neither sufficient shrinkage to qualify for PR nor sufficient increase to qualify for PD, taking as reference the smallest sum LD since the treatment started.

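### Target-lesion progression has no minimum increase in millimetres, so at the smallest target sums the protocol allows, measurement error alone can be confirmed as progression

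*Combined protocol and SAP*

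**What the plan says.** Section 6.1.4.1 calls target-lesion PD when there is "At least a 20% increase in the sum of the LD of target lesions, taking as reference the smallest sum LD recorded" since treatment started, or when new lesions appear. No section adds a minimum increase in millimetres.

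Four rules decide how small the sum can be:
- Section 3.1.3 requires more than one lesion, and "Combined diameter of the lesions must be of size >1.5cm".
- Section 6.1.2 counts lesions as measurable from 10 mm; smaller ones ("<10 mm using spiral CT scan), are considered non-measurable disease") are not.
- Section 6.1.2 removes irradiated lesions from the sum: "Treated lesions and target lesions are mutually exclusive lesions".
- Section 4.1.1 prefers the largest feasible sites for SABR and obliges the physician "to leave at least one site of disease for the purpose of measuring a radiographic response".

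On confirmation, section 2.4.3 says progression is "verified by a second set of imaging at least 6 weeks apart", and section 6.1 says: "The only change from RECIST v.1.1 being implemented in this study is a confirmation of new lesions or progressive disease (PD) by a second scan". In 6.1.4.1 the second-scan phrase follows the new-lesion limb, and the table in 6.1.4.3 lists no confirming scan for target-lesion PD.

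**The concern.** A purely relative threshold shrinks with the sum. A patient with one irradiated lesion of 15 mm and one untreated lesion of 10 mm meets the size criterion and has a target sum of 10 mm. If that lesion shrinks by 30%, the sum is 7 mm. At sums like these, the rise that counts as progression approaches plausible reading error.

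The reference is the smallest sum ever recorded, so a single low reading is kept as the nadir and every later scan is judged against it. False PD would shorten PFS, TTP and response duration, all secondary objectives in section 2.2. PFS is also tested against a historical control in section 11.3. Best overall response is counted only until progression (6.1.4.3), so false PD before a late response could also remove a responder from the primary response rate.

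**Working it through.** **The plan's own figures.** The documents give no false-progression rate to reproduce. The two-stage design in 11.2 (3/17, then 9/33) does reproduce: type I error 0.1966, power 0.8053, early termination 0.427, average N 26.16. The maximum of 33 does not depend on the PD rule.

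**Threshold in millimetres** = 0.20 × nadir sum:
- 7 mm: 1.4 mm
- 10 mm: 2.0 mm
- 15 mm: 3.0 mm
- 20 mm: 4.0 mm
- 25 mm: 5.0 mm
- 50 mm: 10 mm

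**Model for truly stable disease.** Reading S(t) = true sum + normal error with standard deviation SD. Nadir m(t−1) = smallest of S(0) to S(t−1). PD is triggered at scan t if S(t) ≥ 1.2 × m(t−1), and confirmed if S(t+1) ≥ 1.2 × the same nadir. The next scheduled scan is about 8 weeks later, so it can serve as the verification. There were 200,000 simulated patients per row.

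**Inputs.** The documents give no measurement error, so SD = 1.0 mm is an assumption, shown with 0.5 to 1.5 mm. Four scans are the 8-weekly scans of the first eight months in section 4.4. Six scans add two at 12 weeks: 4 × 8 + 2 × 12 = 56 weeks.

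**Check at the first follow-up scan**, 10 mm, SD 1.0: z = 2.0 / (1.0 × √(1 + 1.2²)) = 2.0 / 1.562 = 1.28, a probability of about 10%. The simulation gives 10.1%.

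| True sum | SD of sum | Scans | PD on one scan | PD confirmed on next scan |
|---|---|---|---|---|
| 10 mm | 1.0 mm | 4 | 50% | 15% |
| 10 mm | 1.0 mm | 6 | 70% | 28% |
| 10 mm | 0.5 mm | 6 | 8% | 0.9% |
| 10 mm | 0.7 mm | 6 | 36% | 8% |
| 10 mm | 1.5 mm | 6 | 90% | 54% |
| 15 mm | 1.0 mm | 4 | 18% | 3% |
| 15 mm | 1.0 mm | 6 | 31% | 7% |
| 15 mm | 0.7 mm | 6 | 5% | 0.4% |
| 15 mm | 1.5 mm | 6 | 70% | 28% |
| 30 mm | 1.0 mm | 4 | 0.1% | about 0 |

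If a fifth scan may confirm a rise seen at the fourth, the four-scan confirmed rates at SD 1.0 become 22% (10 mm) and 5% (15 mm).

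**Why confirmation is not enough.** For a true 10 mm sum, one reading at or below 10 / 1.2 = 8.3 mm is enough for an exactly correct later reading of 10 mm to qualify as PD. Two ordinary readings can then confirm each other.

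**Effect of a 5 mm floor.** It binds where 0.20 × nadir < 5 mm, that is, below a 25 mm nadir. For a 10 mm sum over six scans at SD 1.0, false PD falls from 70% to 0.4% on one scan and from 28% to about 0.01% confirmed. At SD 1.5 the figures with the floor are 13% and 1.3%.

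**Several small lesions.** With an error of 1.0 mm per lesion, the SD of three 10 mm lesions is √3 = 1.7 mm. Over six scans one-scan false PD is 18% with or without the floor, since the 20% threshold is already 6 mm. For two 10 mm lesions it falls from 37% to 9%.

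**The case against.** The strongest reply is that the plan already has a safeguard: sections 2.4.3 and 6.1 require progression to be verified at least 6 weeks later. This largely stands. A reader might infer that 2-3 mm of noise is simply called PD, or take the 50-70% one-scan rates as the size of the problem. The documents do not support that; the confirmed rates are the relevant ones. What remains is that the wording of 6.1.4.1 leaves the 20% limb unclear, and that confirmation reduces the error at the smallest sums without removing it.

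Other stronger readings also fail:
- *Target sums are often small.* No section gives their distribution. Up to six untreated lesions may be targets and any number of metastases is allowed. Sums of 10-15 mm are possible; their frequency is unknown.
- *Good responders lose their response.* A response recorded before false PD is kept under 6.1.4.3. Only false PD before a late response touches the response rate.
- *False PD stops IL-2.* Sections 4.2.1 and 4.3 restrict repeat courses to patients without progression, while 5.5.4 leaves continuation after progression to the medical oncologist. These passages must be reconciled; the consequence is not automatic.
- *CT spacing sets the noise.* Section 6.1.3 says scans "should be performed using a 5 mm contiguous reconstruction algorithm", but that is not a measurement error and the calculation does not use it.

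Two further objections stand in part. The 5 mm figure appears nowhere in the documents as a progression threshold, so it is a choice to be justified. A floor in this trial alone may also lengthen PFS slightly relative to the historical control, whose trial used the same criteria according to 6.1. Mandatory confirmation already departs from those criteria, so this is a small cost to state rather than a reason against the change.

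**Conclusion.** The point holds for small target sums. The rule has no absolute minimum, the protocol allows a sum of one 10 mm lesion, and confirmation leaves about 15-28% false progression at 10 mm and 3-7% at 15 mm over four to six scans. These figures assume an SD of 1.0 mm, independent normal errors and truly constant disease. The result is sensitive to the SD. It is essentially nil at 30 mm or more when the SD of the whole sum is 1.0 mm or less.

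The documents give neither the measurement error nor the distribution of target sums, so the bias across the trial cannot be computed. It falls mainly on PFS, TTP and response duration. An effect on the primary response rate is possible only through false PD before a late response, and is not quantified. The change is worth making because it is cheap and acts where the rule is weakest, not because a large bias has been shown.

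**What to change.** In 6.1.4.1, for endpoint classification, define target-lesion PD as at least a 20% increase over the smallest recorded sum LD together with an absolute increase of at least 5 mm. In the same sentence, say that verification at least 6 weeks later applies to this limb as well as to new lesions, in line with 2.4.3 and 6.1, and add it to the 6.1.4.3 table. Since 6.1 calls confirmation the only change from RECIST v1.1, the sponsor should also check the written rule against the version it cites.

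The cost is one or two sentences, with no change to the sample size. True growth of very small lesions is called slightly later, and PFS may lengthen slightly against the historical control in 11.3; the report should say so. The floor mainly protects single small lesions and does little where a sum near 30 mm is made up of several.

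Sections 4.2.1, 4.3 and 5.5.4 should be reconciled separately on what progression means for further IL-2. No treatment rule is proposed here.

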#### 6.1.4.2 Evaluation of Non-Target Lesions

Complete Response (CR): Disappearance of all non-target lesions and normalization of tumor marker level.

Incomplete Response/Stable Disease (SD): Persistence of one or more non-target lesion(s) and/or maintenance of tumor marker level above the normal limits.

Progressive Disease (PD): Appearance of one or more new lesions and/or unequivocal progression of existing non-target lesions

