#### 6.1.4.3 Evaluation of Best Overall Response

The best overall response is the best response recorded from the start of the treatment until disease progression/recurrence (taking as reference for progressive disease the smallest measurements recorded since the treatment started). The subjects best response assignment will depend on the achievement of both measurement and confirmation criteria.

Target Lesions	Non- Target Lesions	New Lesions	Overall Response	Best Response for this Category
-------------------	---------------------------	-------------	---------------------	---------------------------------------

				Also Requires:
CR	CR	No	CR	≥4 wks. confirmation
CR	Non- CR/Non- PD	No	PR	> 4 wks. confirmation
PR	Non-PD	No	PR	
SD	Non-PD	No	SD	documented at least once ≥4 wks. from baseline
PD	Any	Yes or No	PD	
Any	PD*	Yes or No	PD	no prior SD,
Any	Any	Yes	PD	PR or CR
* In exceptional circumstances, unequivocal progression in non-target lesions may be accepted as disease progression.				

Note: Subjects with a global deterioration of health status requiring discontinuation of treatment without objective evidence of disease progression at that time should be reported as "*symptomatic deterioration*". Every effort should be made to document the objective progression even after discontinuation of treatment.

Note: If subjects respond to treatment and are able to have their disease resected, the patient's response will be assessed prior to the surgery.

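### The non-target rule, the best-response table and the 6.1.2 note omit the six-week confirmation of progression that sections 2.4.3 and 6.1 require, so the same scans can be scored PR or PD

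*Combined protocol and SAP*

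**What the plan says.** **Passages that require confirmation.** Section 2.4.3 says that progression is "verified by a second set of imaging at least 6 weeks apart". Section 6.1, which opens by addressing the primary endpoint, names a single departure from RECIST v1.1: "confirmation of new lesions or progressive disease (PD) by a second scan >6wks apart". Its reason is that new lesions may appear early and then regress, and that without a second scan such patients would be counted as treatment failures. Section 6.1.4.1 includes in target-lesion PD "the appearance of one or more new lesions verified by a second scan > 6 weeks apart". Section 6.1.4.4.1 asks for a repeat bone scan for new bone lesions.

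**Passages that do not.** Section 6.1.4.2 defines non-target PD as "Appearance of one or more new lesions and/or unequivocal progression of existing non-target lesions". In the 6.1.4.3 table any new lesion gives PD. The last column sets four-week conditions in the CR, PR and SD rows; for PD it asks only that there was no earlier SD, PR or CR. The 6.1.2 note, on patients whose lesions have all been irradiated, also makes new lesions PD with no second scan.

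**Passages that link this to the response count.** Section 6.1.4.3 defines best overall response as the "best response recorded from the start of the treatment until disease progression/recurrence". It adds that the assignment "will depend on the achievement of both measurement and confirmation criteria". The PR definition in 6.1.4.1 reads in part "taking as reference the baseline sum LD. There can be no appearance of new lesions", and the CR definition has the same bar. Neither says whether a new lesion that was never confirmed counts.

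**The concern.** Response rate is the primary endpoint, and it is judged against two integer cut-offs in section 11.2: stop at 3 or fewer responses in 17, go forward on more than 9 in 33. The rule that turns scans into responses should therefore give one answer. Here an assessor working from the table has no prompt to wait for a second scan before scoring a new lesion as PD, and PD closes the best-response window. That produces the outcome that section 6.1 says the modification was added to prevent.

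The date of a confirmed PD is a smaller gap in the same text. Sections 2.2.2, 2.2.3, 6.1.6 and 6.1.7 date progression for PFS, TTP and response duration, but none says whether a verified progression takes the date of the first or of the confirming scan.

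**Working it through.** **1. One patient under both sets of passages.** Section 6.1.1 requires assessments at 8 and 16 weeks for a patient to be evaluable. Suppose that week 8 shows a new lesion. At week 16 the lesion is gone, the sum of target diameters is at least 30% below baseline, and the other non-target lesions have not progressed.

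| Step | 2.4.3 and 6.1 | 6.1.4.2 and the 6.1.4.3 table |
|---|---|---|
| Week 8, new lesion | Not yet PD; awaits a second scan | PD |
| Week 16, lesion gone | PD not confirmed, never met | PD already recorded; window closed |
| Target shrinkage of at least 30% | Can count as PR | Falls after progression; not counted |
| Best response | PR, if an unconfirmed lesion does not bar it | PD |

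The left column says only that the PR can count, because 6.1.4.1 bars new lesions without qualification. The pattern is narrow: a PR recorded before the new lesion appears is not displaced under either set.

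**2. Reproduce the plan's design.** Inputs from 11.2: p0 = 0.23, p1 = 0.368, 17 patients then 16 more, continue on 4 or more responses, go on 10 or more in 33. With X1 ~ Bin(17, p) and X2 ~ Bin(16, p),

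P(go) = sum over x = 4 to 17 of P(X1 = x) × P(X2 ≥ 10 − x).

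- Early termination at 0.23: P(X1 ≤ 3) = 0.427 (plan: 0.43).
- Average sample size: 17 + 16 × (1 − 0.4272) = 26.16 (plan: 26.2).
- P(go) at 0.23: 0.1966 (limit 0.20).
- P(go) at 0.368: 0.8053 (target 0.80).

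The design reproduces. Nothing in this point disputes it.

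**3. How much one such patient matters.** Fix one patient as responder (s = 1) or non-responder (s = 0) and let the other 32 respond independently with probability p. For a stage-1 patient X1 = s + Bin(16, p); for a stage-2 patient X2 = s + Bin(15, p). The probability that the choice of passage changes the decision is P(go | s = 1) − P(go | s = 0).

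| True RR | Patient in | P(go), counted | P(go), not counted | Difference |
|---|---|---|---|---|
| 36.8% | stage 1 | 0.8759 | 0.7641 | 0.112 |
| 36.8% | stage 2 | 0.8535 | 0.7771 | 0.076 |
| 23% | stage 1 | 0.2959 | 0.1669 | 0.129 |
| 23% | stage 2 | 0.2770 | 0.1725 | 0.104 |

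Averaged over position:

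- At 36.8%: (17 × 0.112 + 16 × 0.076)/33 = 0.095.
- At 23%: (17 × 0.129 + 16 × 0.104)/33 = 0.117.

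**The case against.** The strongest reply is that section 6.1 already settles the matter. It speaks expressly for the primary endpoint, states the confirmation rule generally, and describes almost exactly the patient in the example. Section 2.4.3 exempts no lesion type. Section 6.1.4.1 attaches the condition to new lesions, and a new lesion is the same event in 6.1.4.2. Section 6.1.4.3 itself refers to confirmation criteria. On this view only a cross-reference is missing.

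Much of that stands. A reader might infer that the plan has no governing rule, or that the sponsor must still choose which response count decides. The documents do not support either: 6.1 shows the intended rule for the primary endpoint. What survives is that the table an assessor would use gives a different result, and that 6.1 does not expressly say whether a regressed new lesion still permits CR or PR.

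Section 6.1 also argues that confirmation will not affect the outcome because responses to HD IL-2 are durable. Durability describes how long a response lasts once counted; it does not say whether the patient in the example is counted.

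A reader might also infer that the section 11.3 PFS test against the historical control is materially biased by late dating of PD. The documents do not support that. Sections 2.2.2 and 6.1.6 refer to the first date of documented progression, so first-scan dating is the natural reading, and under it no date is delayed to the confirming scan. They give no control PFS median from which to size a shift. They say of RECIST that it was the system "which was also used by the two randomized trials of HD IL-2 being used as historic controls for this trial"; that those trials lacked a confirmation rule is an inference.

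**Conclusion.** The inconsistency is real and reaches the primary endpoint: 6.1.4.2, the PD and new-lesion rows of 6.1.4.3 and the 6.1.2 note score PD on a single appearance, contrary to 2.4.3 and 6.1. It is a conflict to reconcile, not an undefined endpoint.

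Its size is conditional. Given exactly one patient with the pattern, and independent responses in the others, the passage followed changes the go/no-go decision with probability about 0.08-0.11 at a true RR of 36.8% and 0.10-0.13 at 23%. The documents give no frequency for the pattern, so the unconditional effect cannot be stated. The unstated PD date is a wording gap, and no PFS effect is claimed for it. The correction should be made because it is cheap and the cut-offs are sensitive to single patients.

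**What to change.** 1. Carry the section 6.1 confirmation rule into 6.1.4.2, the PD and new-lesion rows of the 6.1.4.3 table, and the 6.1.2 note.
2. Use one interval. Sections 6.1 and 6.1.4.1 say more than 6 weeks; 2.4.3 and 6.1.4.4.1 allow exactly 6.
3. In 6.1.4.1, say whether confirmation also covers the 20% increase in target lesions, and whether an unconfirmed new lesion that regresses bars CR or PR.
4. State that a confirmed PD is dated at the first scan for PFS, TTP and response duration.
5. Optionally, because 6.1 ties the historic controls to RECIST, also report RR and the 11.3 PFS comparison under unconfirmed RECIST PD as a sensitivity analysis. The 6.1 rule would still decide the primary endpoint.

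The cost is wording for items 1 to 4 and, for item 5, one extra derivation from scans already taken. No further patients or imaging are needed, and the design in 11.2 is unchanged.
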